6.3. Treatment Assignment

The volunteers in this study will enroll in each group of the study sequentially as this is a dose escalation study. Each volunteer will undergo randomization as described in [Section 8.4](#). Each group will be fully enrolled prior to the enrollment of the next group. The description of the FLSC vaccine is noted in [Section 8](#) and [Section 9](#) and the clinical formulation of the products are listed in [Section 9](#). Volunteers in all arms will be immunized by intramuscular injection on Days 0, 28 (week 4), 56 (week 8), and 168 (week 24). Following completion of the immunization schedule, all volunteers will be followed (for an additional 24 weeks) until the end of the trial at 48 weeks as detailed in [Section 6.1.1.3](#).

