6.4. Dose Escalation Criteria

Requirements to begin immunizations in the higher dose groups (Groups 2 and 3) are listed below.

1. Safety data including the visit 4 data (2 weeks after the second immunization) in the 20 volunteers in the lower dose group has been collated and then reviewed by the DSMB.
2. DSMB review is completed, no safety concerns are noted, and approval to enroll the next group is granted.

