6.4.1. Safety Criteria for Adjustment or Stopping Doses

1. If more than 5 volunteers in any group have an unexplained CD4 cell count decline (confirmed by assays at least 4 weeks apart) of greater than 30 percent and corroborated by a similar CD4% decline (>30%), immunizations in that study group will be stopped. No further immunizations will be allowed until after all data are reviewed by the IHV DSMB and the DSMB authorizes immunizations to continue in this group. Follow-up visits for safety will continue during this time. Note that an unexplained drop in CD4 cell count is defined as a decline that cannot be explained by an intercurrent illness or other event known to cause decreased CD4 cell counts.
2. The entire study will be stopped if five or more vaccine related severe (grade 3 or 4) adverse events occur in any group.
3. The volunteer will have immunizations stopped upon the occurrence of an unexpected Grade IV event felt by the investigator to be related to the study vaccine. No further immunizations will be allowed until after all data are reviewed by the IHV DSMB and the DSMB authorizes immunizations to continue in this group. Follow-up visits for safety will continue during this time.
4. The entire study immunizations will be stopped upon the occurrence of one unexpected serious adverse event felt to be related to the study vaccine.

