7.3.4. Reasons for Discontinuation of all Immunizations in the Study

All immunizations across the entire study will be stopped upon the occurrence of 5 or more unexpected Grade 3 or 4 events felt to be related to the study vaccine in any group or a serious adverse event felt to be related to study vaccine in one volunteer as noted in [Section 6.4.1](#) and [Section 6.5](#). Follow-up visits for safety will continue to occur as per study protocol. No further enrollments will occur.

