11.6. Data Safety Monitoring Board

The Clinical Research Unit is experienced in establishing DSMBs in single-site protocols in the participation in single and multi-site clinical trials. Adverse Event Reporting requirements of the IRB, FDA, the NIH Biotechnology Activities, and the industry/private sponsor will be followed. For this trial, IHV has established a DSMB. The DSMB plan will be approved by the IRB prior to implementation.

The Data Safety Monitoring Board (DSMB) will review this trial for safety beginning with the enrollment of the first volunteer into the study. The Board will meet prior to advancement to the next higher dose group as outlined in the protocol to insure that there are no safety concerns. It will also meet approximately every 3 months but can be called together on an ad-hoc basis if a particular patient event calls for immediate attention. At the regularly scheduled (3 month) meetings and the advancement to the higher dose group meetings, the board will review the following:

- All Adverse Events
- Update on all Serious / Study Related Events
- All safety related amendments
- Protocol deviations / exceptions
- Laboratory tests, enrollment numbers, clinical summaries
- Require changes in Standard Operational Procedures for Adverse Events Reporting and Chart Audit as necessary.

All reviews will be of blinded data. However, the DSMB will have access to the envelopes with the treatment assignment of the volunteers to unblind the data should this be needed to ensure the safety of study participants. The DSMB may recommend or mandate changes to the study, and has the power to halt the study if it feels that a volunteer's safety is compromised. The DSMB will provide the Principal Investigator, with a written report detailing its review of the study. The investigator(s) will have the opportunity to respond to the DSMB's report.

Board members will be notified of all internal serious study related, drug related, and/or device related Adverse Events in this study within 48 hours of occurrence via email. Each board member should respond via e-mail, or fax within 48 hours.

A DSMB member who is a physician will be called upon via fax, e-mail, or phone call to discuss any deviations/exceptions a PI may be thinking of requesting prior to approaching the sponsor. This will help to determine if the deviation/exception is necessary and will not compromise the safety of the patient.

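### A CD4 halt in one dose group does not automatically pause higher-dose groups already dosing; their injections continue by default until someone uses a discretionary power

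*Combined protocol and SAP*

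**What the plan says.** Section 6.4.1, item 1, sets the CD4 rule. If more than 5 volunteers in a group have an unexplained fall of over 30% in count and in CD4%, "confirmed by assays at least 4 weeks apart", then "immunizations in that study group will be stopped. No further immunizations will be allowed until after all data are reviewed by the IHV DSMB". The restart has the same scope: it waits until "the DSMB authorizes immunizations to continue in this group". Section 7.3.3 repeats the rule with the same scope, although its threshold is 5 or more.

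Other rules in the protocol are study-wide. Items 2 and 4 of section 6.4.1 act on the whole study for related severe events and for one unexpected related SAE. Section 7.3.4 says "All immunizations across the entire study will be stopped upon the occurrence of 5 or more unexpected Grade 3 or 4 events" judged related in any group. Neither 6.5 nor 7.3.4 adds a CD4 criterion of its own; each refers back to 6.4.1 for the rest.

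Escalation is sequential. Section 6.3: "Each group will be fully enrolled prior to the enrollment of the next group". Section 6.4 requires DSMB review of "Safety data including the visit 4 data (2 weeks after the second immunization) in the 20 volunteers in the lower dose group", and then that "DSMB review is completed, no safety concerns are noted, and approval to enroll the next group is granted". These are conditions for starting a higher-dose group. They say nothing about pausing one that has started.

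On the DSMB, section 11.6 says "It will also meet approximately every 3 months but can be called together on an ad-hoc basis", and gives the board power to halt the study.

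**The concern.** Section 4.5.2 names anti-CD4 autoimmunity as the risk that shapes the design. In a dose escalation, a confirmed CD4 signal at 75 µg is a direct reason to hold 150 µg and 300 µg until the data have been reviewed. As written, the halt stops the dose that produced the signal and leaves the higher doses running.

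The escalation gate cannot close this gap for late declines. It requires lower-dose data at least through Visit 4 (Day 42), before doses 3 and 4 (Days 56 and 168). A signal that emerges after those doses can be confirmed when the next group is already being injected. What is at stake is the higher-dose injections given between the trigger and a decision.

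**Working it through.** The plan gives no figure for this rule, so the check has two parts: the scope of the wording, and a timeline under stated assumptions.

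**Scope.** In 6.4.1, item 1, and 7.3.3, both the stop and the restart name the triggering group. The study-wide rules require events judged vaccine related. Appendix 2 has no CD4 row, so a decline would have to be graded on the general scale (activity limitation, need for intervention) before it could count as Grade 3 or 4. A CD4 halt does not by itself reach a study-wide rule.

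**Inputs from the documents.** Each group has 20 volunteers, 15 on vaccine (Table 3). Doses fall at weeks 0, 4, 8 and 24. CD4 is drawn on Days 70, 84, 112, 182, 196 and 252, among others (Table 4). Recruitment is 36 weeks in the Synopsis and 16 weeks in section 6.1.1.2. The Synopsis dates, November 2015 to May 2018, span 126–135 weeks; less 48 weeks of follow-up that is 78–87, taken as 82.

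**Assumptions.** Enrolment is even, with equal periods per group. Gate review lasts R = 0–4 weeks (R = 0 for the 16-week case). Confirmation is at scheduled draws. The halt is reached at the k-th volunteer, k = 5 to 20.

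**Formulas.** With E the enrolment weeks per group and T the recruitment period, 3E + 12 + 2R = T, because each of two gates waits 6 weeks for the last Visit 4. Group 2 starts at E + 6 + R and Group 3 at twice that. A decline first seen on Day 70 cannot be confirmed on Day 84 (2 weeks later), so it is confirmed on Day 112. The Group 1 post-dose-3 halt is then at week 16 + (k − 0.5)E/20. I count higher-dose injections due in the following 4 weeks.

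**Example.** T = 36, R = 0 gives E = 24/3 = 8, and Group 2 starts at week 14. With k = 20 the halt is at 16 + 19.5 × 0.4 = 23.8. Between weeks 23.8 and 27.8, Group 2 has 5 second doses and 10 third doses due, 15 in all.

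| Recruitment | E (weeks) | Group 2 / Group 3 start (week) | Group 1 post-dose-3 halt (week) | Injections within 4 weeks |
|---|---|---|---|---|
| 36 weeks | 8.0 to 5.3 | 14.0–15.3 / 28.0–30.7 | 17–24 | 15–20 at 150 µg; none at 300 µg |
| about 82 weeks | 23.3 to 20.7 | 29.3–30.7 / 58.7–61.3 | 21–39 | 4–11 at 150 µg once Group 2 has started |
| 16 weeks, R = 0 | 1.3 | 7.3 / 14.7 | 16.3–17.3 | 0–5 at 150 µg; 20 at 300 µg |

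On the 82-week timeline, halts reached before about the 12th volunteer (R = 0) or 15th (R = 4) precede the start of Group 2, and the gate catches them. On the 36-week timeline, shorter windows give 3–8 injections in 1 week and 6–13 in 2 weeks.

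A decline first seen after dose 4 (Day 182) is confirmed at Day 252. With 36-week recruitment, the 4 weeks after such a Group 1 halt hold 5–15 injections at 150 µg and 0–20 at 300 µg. Group 1 has none left to stop.

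**How often the rule fires.** Binomial probabilities, at assumed rates of confirmed decline:

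| Volunteers, rate | 6 or more (6.4.1) | 5 or more (7.3.3) |
|---|---|---|
| 15 vaccinees, 10% | 0.2% | 1.3% |
| 15 vaccinees, 20% | 6% | 16% |
| 15 vaccinees, 30% | 28% | 48% |
| all 20, 5% background | 0.03% | 0.3% |
| all 20, 10% background | 1.1% | 4.3% |

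**The case against.** The strongest defence is that the protocol uses tiered stops (volunteer, group, study) and surrounds them with other brakes. A CD4 halt requires DSMB review of all data before that group resumes. The board can meet ad hoc and can halt the study. Section 13.7 lets the sponsor and Principal Investigator stop if the product may be unsafe, and 11.5.1 leaves discontinuation to the investigator's discretion. Each higher group has its own CD4 rule. All of this stands. But the stopping powers are discretionary, no deadline is set, and a group's own rule acts only after 5 or 6 confirmed cases at the higher dose.

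The 48-hour notice in 11.6 may be said to cover unexplained CD4 declines judged related. Whether it is limited to serious events is ambiguous, so a prompt notice route is arguable. Notice is still not a pause.

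A reader might infer that higher-dose groups are unprotected after a CD4 halt, or that escalation to a new dose would go ahead regardless. The documents do not support either: the brakes above apply, and a group not yet started stays behind the no-safety-concerns condition in 6.4. Conversely, the sentence barring further immunizations, or the title of 7.3.3, might be read as study-wide; the surrounding text confines both to the one group.

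Two limits on the figures also stand. Injection counts are not harm: the benefit of a pause is only those injections the DSMB would later have prevented. And a halt at the 5th volunteer is an extreme: with one placebo in each block of 4 (section 8.4), the first five volunteers cannot all be vaccinees.

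**Conclusion.** The gap is real and narrow. It is a missing default for the interval between a CD4 trigger and a decision, for higher-dose groups already dosing. It follows from the wording and does not depend on the timeline.

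Its size does depend on the timeline. The 4-week figures span 4 to 20 injections at 150 µg on the two longer timelines, and mainly 300 µg injections on the shortest. Three quarters of each count are vaccine (15 of 20), so 15–20 injections means about 11–15 of vaccine. The 16-week case leaves only 16 − 12 = 4 weeks to enrol all 60 volunteers; it is shown because section 6.1.1.2 states it. On the 82-week timeline the gate catches the earlier post-dose-3 halts. Enrolment pattern, review times and decline rates are assumptions.

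The trigger is uncommon unless the true rate is high, and at a 5% background rate an automatic pause would rarely be a false alarm. The change is worth making because it costs little and concerns the risk the protocol itself puts first.

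**What to change.** Add to 6.4.1, item 1, and to 7.3.3: a CD4 halt in any group pauses immunizations and enrolment in that group and in every higher-dose group until an ad hoc DSMB review of all data, and the authorization to resume names each group. What happens at each dose after the review stays with the DSMB.

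State also that doses delayed or omitted because of a safety pause do not count as missed immunization visits under 6.1.1.4, 6.1.1.5 and 7.3.1.1. This is needed because visit windows are ±7 days through dose 3 and ±28 days afterwards, two missed immunizations mean removal, and replacement ends when enrolment closes. With 36-week recruitment, a Group 1 post-dose-3 halt at the 15th to 20th volunteer and R of 0, 2 or 4 weeks, a 4-week pause takes 11–16 of 20 Group 2 volunteers past a dose window. A 6-week pause does so for 15–20, and 2–4 of them miss two doses.

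The cost is a short amendment, using the existing DSMB and the CD4 draws already scheduled. The downside is that, after a rare trigger, higher-dose schedules may be delayed and some doses given outside their window.

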6.4.2. Pharmacokinetic Criteria for Adjustment or Stopping Doses

Not applicable.

6.5. Criteria for Study Termination

Criteria for Termination of Study immunizations in all volunteers.

1. The entire study will be stopped upon the occurrence of an unexpected Grade 3 or 4 event thought to be related to the study vaccine in 5 volunteers as noted in [Section 6.4.1](#). If after review by the DSMB, these events are determined by the DSMB to be study vaccine related, the volunteers would be continued to be followed on the study for safety, but no further immunizations would occur in any of the groups.
2. Individual volunteers may have immunizations halted as listed in [Section 6.4.1](#).

Table 3: Study Design

Phase 1 FLSC Study Immunization Schedule/Volunteer Allocation							
Group	Route of Administration	N Vaccine/Control	Vaccine Dose	Vaccination Schedule in Months (Days)			
				0	1(28)	2(56)	6(168)
1	IM	15	0.25 ml (75 ug)	FLSC/ ALPO4	FLSC/ ALPO4	FLSC/ ALPO4	FLSC/ ALPO4
		5	0.25 ml	Saline	Saline	Saline	Saline
2	IM	15	0.5 ml (150 ug)	FLSC/ ALPO4	FLSC/ ALPO4	FLSC/ ALPO4	FLSC/ ALPO4
		5	0.5 ml	Saline	Saline	Saline	Saline
3	IM	15	1.0 ml (300 ug)	FLSC/ ALPO4	FLSC/ ALPO4	FLSC/ ALPO4	FLSC/ ALPO4
		5	1.0 ml	Saline	Saline	Saline	Saline
TOTALS		60					

Table 4: Schedule of Assessments

STUDY VISIT	0	01	02	03	04	05	06	07	08	09	10	11	12	13	14 ³				
STUDY DAY	-30 TO -3	0	1-2	14	28	29-30	42	56	57-58	70	84	112	168	169-170	182	196	252	294	336
STUDY WEEK	-4 TO -0	0	2	4	6	8	10	12	16	24	26	28	36	42	48				
Informed Consent	X																		
Immunization		X		X		X		X				X							
Complete Medical History and Physical Examination	X																		X
Interval Medical History and Directed Physical Examination(as indicated)		X		X	X		X	X		X	X	X	X		X	X	X	X	
Phone Interview			X			X			X					X					
Dispense diary		X			X			X					X						
Monitor Adverse Events		X	X	X	X	X	X	X	X	X	X	X	X	X	X	X	X	X	X
Blood for Screening Labs: CBC with diff Serum Chemistry, LFT's PT/PTT Hepatitis B Surface Antigen Hepatitis C Antibody ¹ CD4 cell count HIV-1 RNA PCR HIV-1 ELISA/Western blot	X																		X
Pregnancy Test (serum)	X																		
Pregnancy Test (urine)		X			X			X					X						X
Urinalysis	X																		X

STUDY VISIT	0	01		02	03		04	05		06	07	08	09		10	11	12	13	14 ³
Blood for Safety Labs: CBC with diff Serum Chemistry, LFT's CD4 cell count HIV-1 RNA PCR ²		X		X	X		X	X		X	X	X	X		X	X	X	X	
Blood for Serologic Assays/Serum storage	X	X ⁴		X ⁴	X ⁴		X ⁴	X ⁴		X ⁴	X	X ⁴	X ⁴		X ⁴	X	X ⁴	X	X ⁴
Blood for Cellular Immune Response Assays/Storage	X	X ⁴		X ⁴	X ⁴		X ⁴	X ⁴		X ⁴	X	X ⁴	X ⁴		X ⁴	X	X ⁴	X	X ⁴
Total blood volume(ml)	75 ml	64 ml	X	64 ml	84 ml	X	64 ml	84 ml	X	64 ml	84 ml	64 ml	90 ml	X	64 ml	94 ml	64 ml	64 ml	102 ml
Approximate Visit Duration (minutes)	60	60	10	30	60	10	30	60	10	30	60	30	60	10	30	30	30	30	60

Footnotes:

1. If positive Hepatitis C antibody and documentation of negative Hepatitis C PCR can be provided, the volunteer may enroll.
2. HIV RNA PCR will be performed at the screening and end of study visit. Blood will be stored for the PCR at subsequent visits but the assay will not be performed unless there is a concern for acute infection.
3. Visit 14 procedures will also be carried out in the case of early withdrawal/discontinuation.
4. Initially the planned assay days are those marked with a superscript. The other days will be stored for future studies.

Table 5: Blood Draw Flow Sheet

STUDY VISIT	0	01		02	03		04	05		06	07	08	09		10	11	12	13	14 ²
STUDY DAY	-30 TO -3	0	1- 2	14	28	29- 30	42	56	57- 58	70	84	112	168	169- 170	182	196	252	294	336
STUDY WEEK	-4 TO 0	0		2	4		6	8		10	12	16	24		26	28	36	42	48
Immunization		X			X			X					X						
Blood for Screening Labs: CBC with diff Serum Chemistry, LFT's, PT/PTT Hepatitis B Surface Antigen Hepatitis C Antibody CD4 cell count HIV-1 RNA PCR	X																		
Blood for Safety Labs: CBC with diff Serum Chemistry, LFT's CD4 cell count HIV-1 RNA PCR ²		X		X	X		X	X		X	X	X	X		X	X	X	X	X
Pregnancy Test (serum)	3 ml																		
CBC with diff	3 ml	3 ml		3 ml	3 ml		3 ml	3 ml		3 ml	3 ml	3 ml	3 ml		3 ml	3 ml	3 ml	3 ml	3 ml
Serum Chemistry, LFT's,	3 ml	3 ml		3 ml	3 ml		3 ml	3 ml		3 ml	3 ml	3 ml	3 ml		3 ml	3 ml	3 ml	3 ml	3 ml
PT/PTT	3 ml																		3 ml

STUDY VISIT	0	01		02	03		04	05		06	07	08	09		10	11	12	13	14 ²
HIV-1 RNA Quantitative PCR	5 ml	5 ml		5 ml	5 ml		5 ml	5 ml		5 ml	5 ml	5 ml	5 ml		5 ml	5 ml	5 ml	5 ml	5 ml
HBsAg, Hep C Ab	5 ml																		
HIV-1 ELISA/Western blot	5 ml												5 ml						5 ml
CD4 cell count	3 ml	3 ml		3 ml	3 ml		3 ml	3 ml		3 ml	3 ml	3 ml	3 ml		3 ml	3 ml	3 ml	3 ml	3 ml
PBMC stored	30 ml	30 ml		30ml	50 ml		30 ml	50 ml		30 ml	50 ml	30 ml	50 ml		30 ml	50 ml	30 ml	30 ml	50 ml
Serum stored ¹	15 ml	20 ml		20 ml	20 ml		20 ml	20 ml		20 ml	20 ml	20 ml	20 ml		20 ml	30 ml	20 ml	20 ml	30 ml
Total blood volume(ml)	75 ml	64 ml	X	64 ml	84 ml	X	64 ml	84 ml	X	64 ml	84 ml	64 ml	90 ml	X	64 ml	94 ml	64 ml	64 ml	102 ml
Total Study Blood Volume (over 48 weeks):	1125 ml																		

Footnotes:

1. If positive Hepatitis C antibody and documentation of negative Hepatitis C PCR can be provided, the volunteer may enroll.
2. HIV RNA PCR will be performed at the screening and end of study visit . Blood will be stored for the PCR at subsequent visits but the assay will not be performed unless there is a concern for acute infection.
3. Visit 14 procedures will also be carried out in the case of early withdrawal/discontinuation.

7. SELECTION AND WITHDRAWAL OF VOLUNTEERS

7.1. Volunteer Inclusion Criteria

All of the following inclusion criteria must be fulfilled for patients to be eligible for participation in the proposed clinical protocols.

1. Age: 18 to 45 years of age.
2. Sex: Male or Female (female volunteers of child-bearing potential must have a negative serum beta human chorionic gonadotropin (pregnancy) test at time of screening and entry into the study and provide assurance of the use of effective (as judged by the investigator) birth control methods or abstinence beginning at least 60 days prior to the study and during the study)
3. Documented HIV-1 seronegative by ELISA
4. Be in good general health without clinically significant medical history, physical examination findings, or clinically significant abnormal laboratory results (i.e., chronic medical conditions as noted in the exclusion criteria such as cancer as well as any conditions that in the opinion of the investigator might pose a risk to the volunteer)
5. No identifiable risk factor for acquisition of HIV infection (i.e., intravenous drug use/needle sharing, unprotected sex with multiple partners)
6. Negative b-HCG pregnancy test on the day of initial vaccination (women only);
7. Negative screen for Hepatitis B surface antigen (HBsAg);
8. Negative screen for antibodies to Hepatitis C virus (Patient may enroll if patient can provide documentation of negative HCV PCR.)
9. Participant must have a CD4 count within the normal range of the clinical laboratory utilized for the study and a CD4 percentage within 20% of the normal range of the clinical laboratory
10. Laboratory parameters must be within pre-specified limits as defined by exclusion criteria.
11. Volunteers must be willing and able to provide written informed consent to participate in the study.
12. Available for at least 48 weeks of follow-up.

7.2. Volunteer Exclusion Criteria

Any volunteer who fulfills any of the following criteria will not be eligible for entry.

1. High risk behavior for acquisition of HIV within 24 weeks of study entry (i.e., intravenous drug use/needle sharing, unprotected sex with multiple partners)
2. Volunteers with an acute and clinically significant medical event (as determined by the investigator) within the past 30 days of screening.
3. Have active tuberculosis or other systemic infectious process by review of systems and physical examination
4. Have a history of immunodeficiency, autoimmune disease, or use of immunosuppressive medications
5. Current treatment for malignancy other than basal or squamous cell carcinoma of the skin or carcinoma in situ of the cervix
6. Is pregnant

7. History of any chronic illness that would interfere with conduct or completion of study(as determined by the investigator)
8. Have evidence of psychiatric, medical and/or substance abuse problems during the past 24 weeks that the investigator believes would adversely affect the volunteer's ability to participate in the trial
9. Have occupational or other responsibilities that would prevent completion of participation in the study
10. Have received any live, attenuated vaccine except rabies vaccine within 60 days of study entry
11. Vaccine (FDA approved; e.g. influenza, pneumovax, etc) administration within 30 days of immunization with the study vaccine. NOTE: Medically indicated subunit or killed vaccines (e.g., Hepatitis A or Hepatitis B) should be given prior to trial initiation or after completion of the study immunizations. If patient requires immunization, injections should be given more than 2 weeks prior or 2 weeks after study immunization
12. Have used experimental therapeutic agents within 30 days of study entry
13. Have received blood products or immunoglobulins in the past 12 weeks
14. Have a history of anaphylaxis or other serious adverse reactions to vaccines
15. Have previously received an HIV vaccine
16. Volunteers with any of the following laboratory parameters at the screening visit (within 30 days of immunization): Hemoglobin <10 (without having received a blood or RBC transfusion within 30 days prior to laboratory test); neutrophil count <750 cells/mm³; platelet count <50,000/mm³; serum creatinine > 2.0 mg/dL; aspartate aminotransferase (AST) or alanine aminotransferase (ALT) > 3 times the upper limits of normal; total bilirubin > 1.5 mg/dL
17. Pregnant women or women who are breast-feeding; female volunteers of childbearing potential who are not using or willing to use effective (as judged by the investigator) contraceptive methods or abstinence while enrolled in this study.
18. Use of any immune modulators or suppressors within 45 days of study entry including but not limited to agents such as interleukins(e.g. IL-2), interferons (e.g. IFN- α), high dose systemic steroids(e.g. \geq 20 mg prednisone equivalent/day) for > 30 days, thalidomide, filgrastim (G-CSF), sargramostim (GM-CSF), dinitrochlorobenzene (DNCB), thymosin alpha, thymopentin, inosiplex, polyribonucleoside, ditiocarb sodium, cyclosporin, mycophenolate mofetil, methotrexate, and cancer chemotherapy.
19. No other investigational agent within 30 days of study entry
20. Any other condition which, in the opinion of the investigator, might interfere with completion of the study or evaluation of the results
21. Have active Hepatitis B virus infection (positive HBsAg) or Hepatitis C infection(defined as positive antibodies. Patient may enroll if patient can provide documentation of negative HCV PCR.))

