The toxicology studies showed that repeated intramuscular vaccinations with 300 or 900 µg FLSC (with aluminum phosphate adjuvant) was well tolerated in rabbits (up to 5 administrations) and cynomolgus monkeys (up to 4 administrations). The majority of the effects observed in the rabbit toxicity study can be attributed to general inflammation occurring with intramuscular vaccine administration and/or an active immune response towards the antigen. No deleterious effects on the immune system were detected in the cynomolgus monkey with repeat administration of up to 900 µg FLSC (with aluminum phosphate adjuvant). Of most concern is the potential test article related reduction in platelet count with FLSC; however, this finding only occurred in the rabbit with repeat administration of the high dose of FLSC (900 µg), which is 12-fold greater than the proposed starting dose of 75 µg FLSC in the clinic and 3-fold greater than the proposed maximum clinical dose of 300 µg FLSC. Thus, the safety risk of 4 intramuscular administrations of FLSC (with aluminum phosphate adjuvant) to the patient is low.

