6.2. Number of Volunteers

The study population will consist of 60 healthy volunteers without HIV-1 infection who are available for at least 48 weeks of follow-up. Individuals of all races and groups may participate as long as the inclusion/exclusion criteria are met. The inclusion/exclusion criteria have been chosen to minimize risk to all participants. Therefore, those individuals with conditions that might place them at increased risk have been excluded.

Pregnant women and children are excluded from the trial as the safety of this vaccine has not previously been evaluated in humans and the effects on children or the unborn child are not known.

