APPENDIX 2. TABLE FOR GRADING SEVERITY OF ADULT ADVERSE EXPERIENCES

(Adapted from the ACTG and AVEG tables)

ABBREVIATIONS: Abbreviations utilized in the Table:

ULN = Upper Limit of Normal	LLN = Lower Limit of Normal
Rx = Therapy	Req = Required
Mod = Moderate	IV = Intravenous
ADL = Activities of Daily Living	Dec = Decreased

ESTIMATING SEVERITY GRADE

For abnormalities NOT found elsewhere on the Table, use the scale below to estimate grade of severity:

GRADE 1 Mild	Transient or mild discomfort; no limitation in activity; no medical intervention/therapy required
GRADE 2 Moderate	Mild to moderate limitation in activity - some assistance may be needed; no or minimal medical intervention/therapy required
GRADE 3 Severe	Marked limitation in activity, some assistance usually required; medical intervention/therapy required, hospitalizations possible
GRADE 4 Life-threatening	Extreme limitation in activity, significant assistance required; significant medical intervention/therapy required, hospitalization or hospice care probable

SERIOUS OR LIFE-THREATENING AEs

ANY clinical event deemed by the clinician to be serious or life-threatening should be considered a grade 4 adverse experience. Clinical events considered to be serious or life-threatening include, but are not limited to:

seizures, coma, tetany, diabetic ketoacidosis, disseminated intravascular coagulation, diffuse petechiae, paralysis, acute psychosis

MISCELLANEOUS

- > When two values are used to define the criteria for each parameter, the lowest values will occur first.
- > Parameters are generally grouped by body system.
- > Some protocols may have additional protocol specific grading criteria.

PARAMETER	GRADE 1 MILD	GRADE 2 MODERATE	GRADE 3 SEVERE	GRADE 4 POTENTIALLY LIFE THREATENING
HEMATOLOGY				
Hemoglobin	8.0 g/dL - 9.4 g/dL	7.0 g/dL - 7.9 g/dL	6.5 g/dL - 6.9 g/dL	<6.5 g/dL
Absolute Neutrophil Count	1000 - 1500/mm ³	750 - 999/mm ³	500 - 749/mm ³	<500/mm ³
Platelets	75,000 - 99,000/mm ³	50,000 - 74,999/mm ³	20,000 - 49,999/mm ³	<20,000/mm ³
Prothrombin Time (PT)	>1.0 - 1.25 x ULN	>1.25 - 1.5 x ULN	>1.5 - 3.0 x ULN	>3 x ULN
PTT	>1.0 - 1.66 x ULN ULN	>1.66 - 2.33 x ULN	>2.33 - 3.0 x ULN	>3.0 x ULN
Methemoglobin	5.0 - 10.0%	10.1 - 15.0%	15.1 - 20.0%	>20%
CHEMISTRIES				
SODIUM				
Hyponatremia	130 - 135 meq/L	123 - 129 meq/L	116 - 122 meq/L	<116 meq/L
Hypernatremia	146 - 150 meq/L	151 - 157 meq/L	158 - 165 meq/L	>165 meq/L
POTASSIUM				

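### The platelet limit in exclusion 16 (50,000/mm³) lets Grade 1 and Grade 2 thrombocytopenia pass the numeric entry rule, although platelet reduction is the leading toxicology signal; raise it to 100,000/mm³

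*Combined protocol and SAP*

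**What the plan says.** **Entry limit.** Section 7.2, item 16, lists the screening values that exclude a volunteer, among them "platelet count <50,000/mm³; serum creatinine > 2.0 mg/dL". A count of exactly 50,000 passes. Section 7.1, item 10, points back to this list for the numeric limits: "Laboratory parameters must be within pre-specified limits as defined by exclusion criteria".

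**Grading.** Appendix 2 gives platelets of 75,000 to 99,000 as Grade 1, "50,000 - 74,999/mm ³" as Grade 2, 20,000 to 49,999 as Grade 3, and below 20,000 as Grade 4.

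**Toxicology.** Section 4.4.2 states: "Of most concern is the potential test article related reduction in platelet count with FLSC". It adds that the finding arose only in rabbits after repeated 900 µg doses, three times the highest clinical dose, and it concludes that the risk is low.

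**Population.** Section 6.2 says that "the safety of this vaccine has not previously been evaluated in humans", and that "those individuals with conditions that might place them at increased risk have been excluded".

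**Discretion.** Section 7.1, item 4, requires good general health without clinically significant laboratory abnormalities. Section 7.2, item 20, lets the investigator exclude for any other condition that might interfere with completing the study or evaluating its results. Neither gives a platelet count.

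**The concern.** The protocol singles out one laboratory parameter as its main toxicology signal, then sets the entry limit for that parameter at the edge of Grade 3. A volunteer near the limit has little reserve if the rabbit finding carries over to humans. A fall that would leave most healthy people ungraded would take this volunteer into Grade 3. These are healthy people who can expect no benefit from the vaccine, so the justification for enrolling someone with an already reduced count is thin. What is at stake is the safety margin of a rare entrant, not the validity of the trial's comparisons.

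**Working it through.** The plan has no figure of its own to reproduce on this point. The check sets the entry limit against the grading table, then asks how much reserve a low entrant has and how many there would be.

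**Step 1. Limit against grades.** Item 16 passes any count of 50,000 or more. Appendix 2 grades 50,000 to 74,999 as Grade 2 and 75,000 to 99,000 as Grade 1. The numeric rule therefore passes the whole Grade 1 and Grade 2 range. This step needs no assumption.

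**Step 2. Fall needed to change grade.** Fall to the Grade 3 line = 1 − 50,000/baseline. Fall to the Grade 4 line = 1 − 20,000/baseline.

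| Baseline (/mm³) | Fall to Grade 3 line | Fall to Grade 4 line |
|---|---|---|
| 50,000 | 1 − 50/50 = 0% (any fall) | 1 − 20/50 = 60.0% |
| 60,000 | 1 − 50/60 = 16.7% | 1 − 20/60 = 66.7% |
| 75,000 | 1 − 50/75 = 33.3% | 1 − 20/75 = 73.3% |
| 100,000 | 1 − 50/100 = 50.0% | 1 − 20/100 = 80.0% |
| 150,000 | 1 − 50/150 = 66.7% | 1 − 20/150 = 86.7% |

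The 100,000 row is the worst case under the proposed limit. The 150,000 row is for illustration, because the documents give no normal range for platelets.

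**Step 3. How many volunteers.** The documents give no platelet distribution for the recruited population, so I assume a normal one. The expected number of 60 between a and b is 60 × [Φ((b − mean)/SD) − Φ((a − mean)/SD)].

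For mean 250,000, SD 60,000, between 50,000 and 100,000: 60 × [Φ(−2.5) − Φ(−3.33)] = 60 × (0.00621 − 0.00043) = 0.35.

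| Assumed mean / SD | 50,000–60,000 | 50,000–75,000 | 50,000–100,000 | 100,000–150,000 |
|---|---|---|---|---|
| 250,000 / 50,000 | 0.002 | 0.01 | 0.08 | 1.3 |
| 250,000 / 60,000 | 0.02 | 0.08 | 0.35 | 2.5 |
| 230,000 / 60,000 | 0.06 | 0.21 | 0.83 | 4.6 |

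The 50,000–100,000 column is both the expected number of graded entrants and the number of extra screen failures that a 100,000 limit would cause. It is counted before the investigator refuses anyone under inclusion 4 or exclusion 20.

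**The case against.** The strongest reply is that item 16 is a floor and not the whole entry rule. All inclusion criteria must be met, and item 10 does not displace item 4. An investigator who sees 55,000 in a supposedly healthy volunteer can, and probably would, call it clinically significant. This largely stands: the documents permit such an entry but do not compel it. What remains is that the only number the investigator is given marks that count as within limits.

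Three stronger readings are tempting, and the documents do not carry them.

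- **Chance fluctuation could stop the study.** Section 6.4.1 says: "The entire study will be stopped if five or more vaccine related severe (grade 3 or 4) adverse events occur in any group". A reader might infer that one low entrant drifting across 50,000 could drive this rule. But the events must be judged vaccine related, and Section 6.5 states the rule as unexpected related events in 5 volunteers, followed by DSMB review. On that reading one volunteer contributes at most one of the five. The screening and Day 0 counts would also show the low baseline. Entrants close enough to the line to cross it by chance, at 50,000 to 60,000, number about 0.002 to 0.06 of 60.
- **The CD4 rule shows an inconsistency.** Inclusion 9 says: "Participant must have a CD4 count within the normal range of the clinical laboratory utilized for the study", and Section 11 calls the anti-CD4 risk theoretical. Section 4.5.2, however, says that this risk drives the design of the phase 1 safety work, and Sections 6.4.1 and 7.3.3 contain a halt rule based on a CD4 decline above 30%. A normal CD4 baseline serves that rule, so stricter CD4 entry has its own reason.
- **The limit should be the laboratory's lower limit of normal.** With an assumed lower limit of 150,000, this would also turn away about 1.3 to 4.6 per 60 with counts of 100,000 to 150,000. Appendix 2 does not grade those counts, and a fall of 50 to 67% would be needed to reach Grade 3. That goes beyond the problem shown here.

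It is also fair to say that the documents do not report how far rabbit platelets fell or whether they recovered. Safeguards exist: a CBC at every clinic visit (Table 4) and DSMB review of laboratory tests before each escalation and about every 3 months (Section 11.6). These detect a fall after dosing; they do not restore reserve at entry.

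**Conclusion.** The point holds as a minor one. The platelet limit in exclusion 16 coincides with the bottom of Grade 2, so the numeric rule passes Grade 1 and Grade 2 thrombocytopenia in a first-in-human trial whose leading toxicology signal is platelet reduction. That rests on the protocol's text alone. Within the Grade 2 band, the fall needed to reach Grade 3 runs from 0 to 33%; with a 100,000 limit it would be at least 50%.

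The expected frequency is low: about 0.1 to 0.8 of 60 volunteers between 50,000 and 100,000, and 0.01 to 0.21 between 50,000 and 75,000. These figures depend on an assumed normal distribution with mean 230,000 to 250,000 and SD 50,000 to 60,000, before any refusal by judgment. The text does not show that thrombocytopenic volunteers will in practice be enrolled. The case for change is that the gap is plain and closing it costs almost nothing.

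**What to change.** In Section 7.2, item 16, change the platelet limit from <50,000/mm³ to <100,000/mm³. Nobody would then enter with a platelet count that Appendix 2 already grades as an adverse finding. Inclusion 10 picks up the new limit by reference, and inclusion 4 and exclusion 20 stay as they are.

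The cost is one number in one criterion. The screening CBC is already drawn, so there is no extra test or visit. Extra screen failures are about 0.1 to 0.8 per 60 otherwise eligible volunteers under the assumed distributions. The only downside is that an occasional healthy person with a constitutionally low count is turned away.
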